1.0 Background

Prostate cancer (PCa) is the most common non-cutaneous malignancy and the second leading cause of death among men.¹ Transrectal ultrasound guided prostate biopsies are currently the gold standard for the diagnosis of PCa which can be categorized as clinically significant or indolent PCa. Clinically significant prostate cancer (csPCa) is deemed cancer which warrants treatment and is defined according to previously published studies as biopsy Gleason score ≥ 7 or maximum cancer core length ≥ 5 mm.² Indolent PCa is considered cancer which does not require treatment with patients placed on active surveillance and is defined by the modified Epstein criteria as biopsy Gleason score ≤ 6 , PSA density ≤ 0.15 , ≤ 2 positive cores, and unilateral cancer).^{2,3} Given concerns regarding the overtreatment of indolent PCa, efforts to improve the diagnosis of csPCa and limit diagnosis of indolent disease are needed.⁴

Standard in-office prostate biopsies using transrectal ultrasound guidance are random, non-diagnostic and imprecise in detecting PCa. Moreover, standard biopsies may miss csPCa. With multi-parametric magnetic resonance imaging (mpMRI), we now have a way of increasing the detection of csPCa while decreasing the detection of indolent disease. Using the mpMRI and scoring methodology called the prostate imaging reporting and data system (PIRADS v2), lesions suspicious for PCa and csPCa can be categorized as: 1: very low, 2: low, 3: intermediate, 4: high, and 5: very high risk of csPCa.⁵ Studies using mpMRI recommend prostate biopsy of mpMRI lesions with PIRADS ≥ 3 .^{2,5,6}

The Division of Urology has introduced a powerful new solution for analysis, planning and targeted biopsy of the prostate. This consists of using DynaCAD for Prostate mpMRI and the UroNav fusion biopsy system- a comprehensive solution which offers a cutting edge imaging option for many patients with clinical suspicion for harboring PCa mainly by elevated and/ or rising prostate specific antigen (PSA) levels. Targeted MRI/Ultrasound biopsy is poised to become the new standard in PCa diagnosis at UTMB.

Presently at UTMB, if patients have a mpMRI and region of interest identified (usually mpMRI obtained after prior negative biopsy or in patients deemed to have indolent disease by standard prostate biopsy and to be placed on active surveillance) then they are referred for consideration of targeted biopsy with UroNav.

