5.0 Study Procedures

Study population and design:

Eligible patients referred to the Division of Urology will be randomly assigned to one of the following arms: **arm A (mpMRI+ group)**, mpMRI prior to transperineal mpMRI-targeted prostate biopsy; **arm B (Standard group)**, TRUS-guided transrectal 12-core prostate biopsy.

In arm A, all patients with positive mpMRI evidence of lesions suspicious for PCa, i.e. PI RADS ≥ 3 will be submitted to transperineal MRI-targeted prostate biopsy (arm A mpMRI+). In cases of negative mpMRI results i.e. PI RADS < 3, arm A patients will

undergo TRUS-guided transrectal 12-core prostate biopsy (arm A mpMRI-)(refer to figure on page 9).

[figure not shown]
The present randomized clinical trial will compare the outcomes between the two arms.

Primary End-Points: The primary end point will be the comparison of detection rates csPCa between arm A mpMRI+ and arm B. csPCa will be defined according to the Standards of Reporting for MRI-targeted Biopsy Studies (START) criteria for targeted biopsy Gleason Score ≥ 7 or maximum cancer core length (CCL) ≥ 5 mm and the updated Epstein criteria for standard biopsy (Gleason score ≥ 7 , PSA density ≥ 0.15 , Gleason score ≥ 2 positive cores, and bilateral cancer).^{2,3} Patients will be enrolled in an intention to treat trial (See Section 9.1 Statistical Considerations).

Secondary End-Points: The secondary end points will be:

- i. Comparison of the overall detection rate of PCa and csPCa between arm A mpMRI+, arm A mpMRI-, and arm B and
- ii. Comparison of complication rates (Table 2) between arm A mpMRI+ and arm B.

If the primary end point is reached, the study will continue and remain ongoing to examine the remaining secondary end points.

Patients will be consented by Urology providers (IRB approved Co-Investigators and collaborators).

Randomization and data collection will be done by [REDACTED] [REDACTED] (study coordinator) into a REDCap generated case form (SEE APPENDIX). Study coordinator will provide de-identified data for statistical data analysis and will have master file, in password protected computer, which will link the PHI to subject ID (will be assigned by the study coordinator). After the completion of statistical analysis the master file will be deleted permanently.

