Data analysis will be done by [name] (Department of Surgery analyst) supervised by [name] (PI) and statistical analysis collaborators ([name], IRB approved). Data to be analyzed will be de-identified will have no protected health information (PHI) including patient name, medical record number or date of birth.

PRE-PROCEDURE EVALUATION (within 2 months from study enrollment)

Patients are going to be evaluated at the time of office appointment by the PI and Study Collaborators

- Screening-Patients with elevated level of Prostate-specific antigen (PSA >1 ng/ml but <15 ng/ml), will be screened for research study participation by the urology providers (Co-Investigators) and [name] (PI).
- Inclusion/ Exclusion Criteria
- Consent- Patient having all the inclusion and no exclusion criteria for eligibility will be approached with research consent for participation by the urology providers (Co-Investigators) and [name] (PI).
- Demographics
- Medical History
- Surgical History
- Clinical Stage/ Digital Rectal Exam
- Vital Signs
- Physical Exam
- MRI PI-RAD Score (Grade System to classifying prostate cancer , using Pre-Procedure MRI (within 2 months from consenting & randomization))- only required for arm A
- Gland Volume (Calculated from the mpMRI and/or Ultrasound -within 2 months from consenting & randomization)
- Prostate specific antigen (PSA)

PROCEDURE EVALUATION (Surgical procedure)

Patient will undergo prostate biopsy in arm A or arm B as assigned by the randomization card

- A. Transperineal mpMRI-targeted prostate biopsy (arm A mpMRI+) (Procedure will be performed in operating room):** mpMRI-targeted prostate biopsy is standard of care and will be performed using the UroNav transperineal fusion system by a single urologist ([name]). [name] has >1 yr experience in performing mpMRI-targeted prostate biopsies. All patients will receive one dose of Ancef intravenous antibiotic at time of surgery (Vancomycin 1gm intravenous for penicillin/cephalosporin allergies or prior history of orthopedic hardware implanted within 2 years) to cover skin flora and may add additional antibiotic if prior documented UTI(s) in past then antibiotic may be tailored according to those culture(s) sensitivities) to cover enteric flora as well. All patients will receive an enema until result to be performed the morning of prostate biopsy.

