The gland and the regions of interest will be contoured, and the prostate contour will be fused in real time with the TRUS image. Biopsies will be performed via a transperineal approach in the operating room. The patient will be placed in dorsal lithotomy position. mpMRI-targeted biopsies will be performed on regions of interest, and three to six cores will be obtained for biopsy from each lesion and is standard of care according to START criteria for targeted biopsy.

Multiparametric magnetic resonance imaging (mpMRI)

All of the patients in arm A will undergo mpMRI according to the European Society of Urogenital Radiology guidelines. The Prostate Imaging–Reporting and Data System (PI-RADSv2) classification (1-5) will be used to describe the lesions found: 1: very low, 2: low, 3: intermediate, 4: high, and 5: very high risk of csPCa. ⁵ The mpMRI will be performed at two centers with a 3-T scanner using a 32-channel phase array coil or four-channel phase array coil. Two experienced radiologists will analyze the mpMRI findings. Lesions with a PI-RADS score of ≥ 3 will be considered suspicious for PCa.

In cases of negative mpMRI results, arm A patients will undergo TRUS-guided transrectal 12-core prostate biopsy (arm A mpMRI–) in an identical fashion as described in arm B. Urologists (PI and Co-Investigators) will obtain SOC informed consent and perform the TRUS biopsies.

[name] will collect the biopsy sample in case of positive mpMRI results (arm A mpMRI+) and it will be sent out to pathology lab at UTMB for analysis, as SOC.

Please Note: Patients having positive mpMRI results will be referred to [name], by their primary urology (Co-Investigators and collaborators) providers, only after patients provide written consent to participation. Primary Urology (Co-Investigators and collaborators including [name]) providers will consent the patients.

- B. TRUS-guided transrectal prostate biopsy (arm B) (Procedure will be performed in Clinic):** TRUS-guided transrectal prostate biopsy will be performed using a disposable 18-gauge biopsy gun with a specimen size of 18–22 mm (Bard Medical, Covington, GA, USA) by Urology providers (Co-Investigators and [name]

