- Maximum cancer core length (mm)- Based on the biopsy report will be available 2-4 weeks post-procedure
- Adverse event assessment- Can be done by telephone or clinical visit, usually 2-4 weeks post biopsy procedure

Table 2. Schedule of Events

Variables (Both Arm A and Arm B)	Pre-Study (within 2 months from consent and randomization)	Biopsy	Post-Biopsy Follow-up/Study End (within 2-4 wks from biopsy) Follow-up can be done by telephone or clinical visit)
Informed consent*	X		
Demographics	X		
Medical History	X		
Surgical History	X		
Clinical Stage/digital rectal exam	X		
Vital signs	X		
Height	X		
Weight	X		
PSA	X		
MRI PI-RADS (Arm A)	X	X	
Gland volume (MRI- Arm A or US- Arm B)	X	X	
Diagnosis of Prostate Cancer			X
Serum creatinine***	X		
Diagnosis of Clinically Significant Prostate Cancer**			X
Gleason score			X
Total cancer core length (mm)			X
Maximum cancer core length (mm)			X
UADE*		X	X

* Indicates study-only activity.

All other procedures/tasks are standard of care. Prostate specific antigen (PSA), Digital rectal examination (DRE), Prostate Imaging Reporting and Data System (PI-RADS), transrectal ultrasound (TRUS), Unanticipated Adverse Device Event

**Clinically significant PCa defined as targeted biopsy Gleason Score \geq or maximum CCL \geq 5 mm and the updated Epstein criteria for SB.

*** The serum creatinine assessment will be performed no more than one month prior to randomization.

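### PSA density for the standard-biopsy csPCa rule would use MRI volume in arm A mpMRI-negative men and ultrasound volume in arm B; the effect is small and avoidable

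*Combined protocol and SAP*

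**What the plan says.** - **Volume source, schedule of events (Section 5.0, Table 2):** "Gland volume (MRI- Arm A or US- Arm B". The row is ticked at both the pre-study and the biopsy visit.
- **Volume source, pre-procedure evaluation (Section 5.0):** "Gland Volume (Calculated from the mpMRI and/or Ultrasound -within 2 months from consenting & randomization". There is no split by arm.
- **csPCa on targeted biopsy (Section 5.0, primary end point):** "criteria for targeted biopsy Gleason Score ≥ 7 or maximum cancer core length (CCL) ≥ 5 mm". No volume is needed.
- **csPCa on standard biopsy (same paragraph):** "the updated Epstein criteria for standard biopsy (Gleason score ≥ 7 , PSA density ≥ 0.15", followed by further items on positive cores and bilateral disease.
- **csPCa in Section 1.0:** "biopsy Gleason score ≥ 7 or maximum cancer core length ≥ 5 mm". Again there is no density term. Density at 0.15 does appear in that section's definition of indolent cancer.
- **Primary contrast (Section 5.0):** "The primary end point will be the comparison of detection rates csPCa between arm A mpMRI+ and arm B". Secondary end point (i) adds arm A mpMRI-negative men. Section 9.0 makes intention to treat the main analysis for Aim 1.
- **Use of TRUS (Section 5.0):** arm A mpMRI-negative men and arm B men have the same TRUS-guided 12-core biopsy. In arm A mpMRI+ men, "the prostate contour will be fused in real time with the TRUS image".

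**The concern.** PSA density is PSA divided by gland volume. If the volume comes from MRI in one arm and ultrasound in the other, any systematic difference between the methods moves men across 0.15 in one arm and not in the other. The exposed comparison is between arm A mpMRI-negative men and arm B men. They have the same biopsy and, as standard biopsies, fall under the same csPCa rule, yet one input to that rule would be measured differently. The targeted and standard rules also differ from each other, but that is a separate problem. Here the rule is the same and its input differs.

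At stake are secondary end point (i), insofar as it sets mpMRI-negative men against arm B, and an intention-to-treat csPCa rate for arm A, which includes those men. The two statements of volume source in Section 5.0 also disagree, and neither says which recorded volume enters PSA density.

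**Working it through.** **1. The plan's own figures do not depend on volume.** The pooled two-proportion formula for 18.1% versus 48.1%, one-sided 0.05 and 80% power, gives

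n = [1.645·√(2 × 0.331 × 0.669) + 0.842·√(0.181 × 0.819 + 0.481 × 0.519)]² / 0.30² ≈ 29.4.

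That is 30 per arm or 60 in total, against the stated 62. The inflation 72 / 0.90 = 80 matches. Nothing below changes 62, 72 or 80.

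**2. Where density enters csPCa.**

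| Group | csPCa rule | Density used? | Volume source in Table 2 |
|---|---|---|---|
| Arm A mpMRI+ | targeted | no | MRI |
| Arm A mpMRI-negative | standard (inferred: same biopsy as arm B) | yes | MRI |
| Arm B | standard | yes | ultrasound |

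The mismatch therefore affects only the second row against the third.

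**3. How many arm A men are exposed.** Section 9.0 assumes about 25% of arm A is MRI-negative: 0.25 × 36 = 9 men (0.25 × 40 = 10 with the dropout allowance).

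**4. One borderline man.** With PSA 6 ng/ml and volume 40 ml, density is 6 / 40 = 0.150. A volume read 10% smaller gives 6 / 36 = 0.167; read 10% larger it gives 6 / 44 = 0.136. The method alone can decide the side of the cut-off.

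**5. Share of men who cross (assumption).** The documents give no MRI-versus-ultrasound volume difference and no PSA or volume distribution. I simulated lognormal PSA (median 5, 6 or 7 ng/ml, SD of log 0.5, truncated to the eligible 1 to 15) and lognormal volume (median 40 or 50 ml, SD of log 0.4), then rescaled volume. The 29.5% cancer rate is the overall detection on standard biopsy in the cited randomised trial (Section 1.0), applied here to MRI-negative men.

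| One method reads smaller by | Rise in P(density ≥ 0.15), points | × 9 men | × 9 × 29.5% |
|---|---|---|---|
| 0% | 0 | 0 | 0 |
| 5% | 2.7–3.4 | 0.2–0.3 | 0.07–0.09 |
| 10% | 5.7–6.9 | 0.5–0.6 | 0.15–0.18 |
| 15% | 9.0–10.7 | 0.8–1.0 | 0.24–0.28 |

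If volume is read larger by 5%, 10% or 15%, the probability falls by 2.4–3.2, 4.7–6.2 or 6.7–9.2 points, so the size is similar.

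**6. What one reclassified man would do.** Section 9.0 expects 4% csPCa in MRI-negative men: 0.04 × 9 = 0.36 men. One change of status moves that group's rate by 1/9 = 11 points, the whole-arm A rate by 1/36 = 2.8 points, and the mpMRI+ rate by 0. The expected whole-arm A rate is 0.75 × 48% + 0.25 × 4% = 37%, of which MRI-negative men supply 1 point.

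**7. What cannot be computed.** The standard-biopsy items are joined by a conjunction, and one of them reads as a Gleason score of at least 2 positive cores. If all items must hold, density matters only when the others are met. If any one suffices, it matters only when the others are not. The number of men whose csPCa status turns on density therefore cannot be derived.

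**The case against.** The strongest reply is that almost nothing is at stake. Four parts of it stand:

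- The targeted-biopsy rule needs no volume, so the primary contrast as written is unaffected.
- The expected effect is below one man, in a trial sized for a 30-point difference.
- The exposed comparison is not randomised. MRI-negative men are selected by their scan, and the plan expects 4% csPCa there against 18.1% in arm B. That gap dwarfs any volume effect. Section 9.0 also treats the non-intention-to-treat analyses under Aim 2 as sensitivity analyses.
- The documents do not show that the two methods differ at all, and the pre-procedure list would permit one common source. That the density input differs by arm is a fair inference from Table 2, not a stated rule.

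A reader might infer from Table 2 that the primary result is biased, or apply the crossing rates to a whole arm and expect 1 to 4 of 36 men to be affected (2.7% × 36 = 1.0; 10.7% × 36 = 3.9). Neither is supported. Density is not part of csPCa for the roughly 75% of arm A who have targeted biopsy, so in arm A the right multiplier is about 9. Indolent cancer also uses density, but its classification is not a listed end point.

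The reply does not remove the point. The two passages on volume source conflict, Table 2 ties the source to the randomised arm, and TRUS is in use at every biopsy, so the difference is unnecessary.

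**Conclusion.** The point holds in a limited form. As Table 2 is written, the PSA density input to the standard-biopsy csPCa rule differs by arm for about 9 of 36 arm A men. It affects their comparison with arm B in secondary end point (i) and an intention-to-treat arm A total. For a volume difference of 0% to 15%, 0 to about 1 of these men would cross 0.15, and about 0 to 0.3 would both cross and have cancer.

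This rests on the assumed PSA and volume distributions, the plan's 25% MRI-negative share, and 29.5% cancer detection. The last is probably high for MRI-negative men, given the 4% csPCa expected there. The number changing csPCa status is no larger, but cannot be stated. The matter is worth correcting because correction is nearly free; it is not a threat to the trial's main conclusion. Priority: consider.

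**What to change.** Reconcile Table 2 with the pre-procedure list in Section 5.0. Name TRUS volume at biopsy, calculated by one stated formula, as the only volume used for PSA density wherever the standard-biopsy rule applies: arm B and arm A mpMRI-negative men, and all men if density is used for them. Keep MRI volume in arm A as a descriptive variable, and repeat the density classification with it as a sensitivity check.

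The cost is one line in Table 2, one case-form field and one extra recorded value in arm A. No procedure is added and no sample size changes. It should be settled before data collection, because a TRUS volume not recorded at biopsy may not be recoverable.

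An alternative is to apply one csPCa definition without PSA density, such as the one in Section 1.0, to all men. That would make this point moot for csPCa, though not for any indolent classification that uses density.

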6.0 Study Product Description

The actual working elements of the UroNav fusion biopsy system includes the UroNav mobile workstation cart, ultrasound cart and the electromagnetic field generator which connects to the patient bed by a mobile arm. The electromagnetic field generator in combination with a navigation sensor mounted to the TRUS transducer merges the mpMRI images with live TRUS guidance to accurately biopsy the prostate. As previously mentioned, UroNav provides support for transrectal biopsy procedures but *now* has the capability to perform biopsy via a transperineal approach. The UroNav fusion-guidance for transperineal biopsy requires the transperineal stepper which holds the TRUS probe and a standard biopsy grid plate equipped with UroNav universal sensors to precisely perform biopsies. Invivo supports both UroNav and DynaCad which UTMB has recently acquired and the Department of Radiology currently has been working with for many years, respectively. DynaCad is a software used in the radiology suite which exports diagnostic 3D information from a prior mpMRI exam to discern the prostate gland and MR-suspicious lesions.

A detailed UroNav Brochure is attached with IRB submission for review and will be provided to patients (SEE APPENDIX).

7.0 Adverse Events or Unanticipated Problems involving Risk to Participants or Others

Table 3. Complications associated with prostate biopsy

Common (greater than 1 in 10)	Occasional (between 1 in 10 and 1 in 50)	Rare (less than 1 in 50)

 •Blood in your urine for up to 10 days. •Blood in your semen for up to 6 weeks; this is harmless and poses no risk to you or any sexual partners. •Bruising in your perineal area. •Urinary infection (10% risk). •Sensation of discomfort due to bruising. •Haemorrhage(bleeding) preventing you from passing urine (2% risk). 	
 •Blood infection (septicaemia) needing hospitalisation (2% risk). •Haemorrhage (bleeding) needing hospitalisation (1% risk). •Failure to detect a significant cancer of the prostate. •The procedure may need to be repeated if the biopsies are inconclusive or your PSA level rises further. •Inability to pass urine (retention of urine). 	
 •Hospital-acquired infection •Colonisation with MRSA (0.9% - 1 in 110). •MRSA bloodstream infection (0.02% - 1 in 5000). •Clostridium difficile bowel infection (0.01% - 1 in 10,000). 
Please note: The rates for hospital-acquired infection may be greater in “high-risk” patients. This group includes, for example, patients with long-term drainage tubes, patients who have had their bladder removed due to cancer, patients who have had a

		long stay in hospital or patients who have been admitted to hospital many times.
--	--	----------------------------------------------------------------------------------

Complications associated with MR-Gadolinium:

The contrast material used in MRI called gadolinium is less likely to produce an allergic reaction than the iodine-based materials used for x-rays and CT scanning. Very rarely, patients are allergic to gadolinium-based contrast materials and experience hives and itchy eyes. Reactions usually are mild and easily controlled by medication. Severe reactions are rare.

Nephrogenic systemic fibrosis (NSF), a thickening of the skin, organs and other tissues, is a rare complication in patients with kidney disease that undergo an MR with contrast material. Gadolinium-based contrast material may be withheld in some patients with severe kidney disease.

Adverse Event:

For the purposes of this study, pre-planned interventions noted at baseline are not considered AEs.

Adverse Events (AEs) collected in this study will be limited to death post biopsy procedure, serious injury (life threatening, results in permanent impairment of body functions or permanent damage to a body structure, or necessitates medical or surgical intervention to preclude permanent impairment of body functions),

Any unanticipated adverse device event will be recorded and reported to the IRB within 10 business days.

AE/SAE information must be collected up until subject's completion of the study. In the case of death or serious injury, Investigator or study coordinator must report to IRB as soon as possible within 10 business days after first learning the event.

Collection of all AEs, to be reported as follows:

- i) all serious adverse events and/or unanticipated problems involving subjects will be reported as required per the UTMB IRB Policies and Procedures, Section 8; and
- ii) All other adverse events will be recorded on an excel spreadsheet and submitted with each continuing review.

Serious Adverse Event (SAE):

An SAE is defined as an AE that meets one of the following conditions:

- Death during the period of protocol defined surveillance
- Life-threatening event (defined as a subject at immediate risk of death at the time of the event)
- An event requiring inpatient hospitalization or prolongation of existing hospitalization during the period of protocol defined surveillance
- Results in congenital anomaly or birth defect
- Results in a persistent or significant disability/incapacity
- Any other important medical event that may not result in death, be life threatening, or require hospitalization, may be considered a serious adverse experience when, based upon appropriate medical judgment, the event may jeopardize the subject and may require medical or surgical intervention to prevent one of the outcomes listed above. Examples of such medical events include allergic bronchospasm requiring intensive treatment in an emergency room or at home, blood dyscrasias or convulsions that do not result in inpatient hospitalization, or the development of drug dependency or drug abuse.

All SAEs will be:

- recorded on the appropriate SAE CRF
- followed through resolution by a study clinician
- reviewed and evaluated by a study clinician

Unanticipated Adverse Device Events (UADEs):

An UADE is “any serious adverse effect on health and safety or any life-threatening problem or death caused by, or associated with, a device, if that effect, problem, or death was not previously identified in nature, severity, or degree of incidence in the investigational plan or protocol., or any other unanticipated serious problem associated with a device that relates to the right, safety, or welfare of subjects. (21 CFR 812.3(s)).”The principal investigator will submit to the reviewing IRB a report of any UADE occurring during an investigation as soon as possible, but in no event later than ten (10) days after the investigator learns of the effect. All UADEs must be documented by the investigator including the date of consent, a complete description of the event, possible reason(s) for the event, severity, duration, concurrently with appropriate CRF.

Reporting Procedures

Any AE considered serious by the PI ([name]) or Co-PI ([name]) or which meets the aforementioned criteria must be submitted on the SAE form to the IRB in accordance with IRB policies and procedures.

The study PI ([name]) or Co-PI ([name]) will complete Serious Adverse Event Assessment Form within the following timelines:

- All deaths and immediately life-threatening events, whether related or unrelated, will be recorded on the Serious Adverse Event Form within 72 hours of awareness.
- Serious adverse events other than death and immediately life-threatening events, regardless of relationship, will be reported within 10 days of becoming aware of the event.

All SAEs will be followed until satisfactory resolution or until the PI ([name]) or Co-PI ([name]) deems the event to be chronic or the patient to be stable.

Study related risks include loss of confidentiality.

